7.0 TREATMENT PLAN

TREATMENT	PAZOPANIB RUN-IN ^A	CYCLES 1 AND 2 ^B	CYCLES 3 AND 4 ^C	PRE- OP RT ^D	SURGERY ^E	CYCLES 5 AND 6 ^B	POST-OP RT ^F
DOXORUBICIN		75 MG/M2 CIVI OVER 3 DAYS, EACH CYCLE WEEKS 3-8	75 MG/M2 CIVI OVER 3 DAYS, EACH CYCLE WEEKS 9-14	WEEKS 16-21	2-4 WEEKS AFTER COMPLE- TION OF PRE- OPERATIVE THERAPY	75 MG/M2 CIVI OVER 3 DAYS, EACH CYCLE 2-4 WEEKS AFTER SURGERY	2-4 WEEKS AFTER COMPLETION OF CHEMO-THERAPY
IFOSFAMIDE		2 GM/M2 IV, DAYS 1-5, EACH CYCLE WEEKS 3-8 (6-DAY WASHOUT AFTER PAZOPAN -IB	2 GM/M2 IV, DAYS 1-5, EACH CYCLE WEEKS 9-14			2 GM/M2 IV, DAYS 1-5, EACH CYCLE 2-4 WEEKS AFTER SURGERY	

TREATMENT	PAZOPANIB RUN-IN A	CYCLES 1 AND 2B	CYCLES 3 AND 4C	PRE- OP RT D	SURGERY E	CYCLES AND 6B 5	POST-OP RTF
MESNA^I		AFTER EACH DOSE OF IFOS	AFTER EACH DOSE OF IFOS			AFTER EACH DOSE OF IFOS	
PAZOPANIB OR PLACEBO	800 MG PO DAILY, WEEKS 1-2						
PAZOPANIB MAINTEN- ANCE^G							1 WEEK AFTER COMPLETION OF CHEMO/RT (DURATION 52 WEEKS)

A Pazopanib versus placebo run-in 14 days

B Chemotherapy cycles every 21 days. Cycle 1 may not commence until a 6 day washout period of pazopanib has occurred.

C Cycles 3 and 4 will only be given if there is a response to chemotherapy identified on imaging after cycles 1 and 2.

D Pre-operative radiation administration, when given, will consist of external beam 50 Gy in 25 fractions of 2 Gy/fraction over 5 weeks. If the target volume encompasses sensitive structures such as bowel or lung, the dose can be reduced to 45 Gy in 25 fractions of 1.8 Gy without protocol violation.

E Surgery should be planned for 2-4 weeks after completion of pre-operative therapy. Any planned post surgical adjuvant chemotherapy should be initiated only after adequate wound healing has been achieved. Patients who require a delay of greater than 10 weeks from the initial surgery due to inadequate wound healing will be removed from further protocol therapy.

F Post-operative radiation administration, when given, will consist of external beam 50 Gy in 25 fractions of 2 Gy/fraction over 5 weeks, followed by 10 Gy boost (in 5 fractions) to a reduced, or boost, volume. For contaminated or close margins, the boost dose will be 10 - 16 Gy; for microscopically positive margins, 16 - 20 Gy, and for grossly positive margins, 20 – 26 Gy.

For patients who received pre-operative radiation, but have positive surgical margins, 16 – 20 Gy (2Gy x 8 - 10 fractions) will be given by external beam following any planned adjuvant chemotherapy.

G Pazopanib may be resumed 1 week after completion of post-operative therapy (chemotherapy +/- radiation) for those randomized to the treatment who had a response by imaging, to be continued for 1 year. Unblinding occurs during the first post-op visit after surgery.

H PEG-Filgrastim should be administered approximately 24-48 hours after completing chemotherapy. 10 days of filgrastim may be substituted.

I Mesna will be given at 400 mg/m². Post IFOS doses will be at 4 hours and 8 hours (+/- standard clinical dosing windows)

7.1 Agent Administration

7.1.1 Pazopanib Administration

Subjects will be randomized to receive either pazopanib 800 mg orally daily or placebo for 14 days as a Run-in period, prior to beginning neoadjuvant chemotherapy with doxorubicin and ifosfamide. Doses of pazopanib/placebo will be taken fasting (at least 1 hour prior and/or 2 hours after).

Subjects deemed to be responders to pazopanib preoperative therapy (defined in **Section 11.3**), will have the option to receive one year of therapy with pazopanib 800 mg orally daily following completion of surgery and post-operative adjuvant treatments.

Treatment Regimen

Treatment will be administered on an outpatient basis. Subjects receive pazopanib versus placebo at a dose of 800 mg/day (four 200-mg tablets or two 400 mg tablets; dose modification will be accomplished by combining 200-mg tablets as necessary). Subjects are instructed to swallow tablets once a day (preferably in the morning) on an empty stomach, either 1 hour before or 2 hours after food with about 1 cup (240 mL) water. Tablets should be swallowed whole; they must not be chewed, broken, or crushed. Treatment continues until one of the criteria in **Section 7.3** applies.

For the subjects who will have intensive pharmacokinetic analyses performed during pazopanib maintenance, subjects should wait to take the pazopanib on-site (observed dose by study personnel). Subjects should either wait to eat on-site (1 hour after pazopanib dosing) or make sure to eat at least 2 hours before the planned time of pazopanib dosing for that day.

Subjects will be provided with a Medication Diary for pazopanib, instructed in its use, and asked to bring the diary with them to each appointment. A new copy of the Medication Diary will be given to subjects whose dose is reduced due to AEs. Prior to the scheduled study visit, subjects will be reminded to document the exact time of pazopanib dosing the day before blood is drawn for measurement of trough concentrations. Subjects will also be reminded not to take their morning pazopanib dose until after the blood draw for trough concentrations has been completed.

All prescription and over-the-counter medications as well as alternative medicines that have been taken within 4 weeks prior to the first dose of pazopanib must be fully documented in the Case Report Form (CRF; indication, dose information and dates of administration). The Investigator or a designee must be informed as soon as possible about any new medication taken from the time of screening until the end the study; these new medications will be fully documented in the CRF (indication, dose information, and dates of administration).

All concomitant medications taken during the study will be recorded in the CRF with indication, dose information, and dates of administration.

Precautions/Warnings

Certain drugs which induce or inhibit cytochrome P450 enzymes are prohibited. **Medical personnel must refer to the list of prohibited agents in Section 7.4 prior to administering treatment.**

Certain drugs which are listed as “use with caution” should be avoided if possible, but if necessary, subjects who receive these medications should be closely monitored for AEs. **Medical personnel must refer to the list of “use with caution” agents in Section 7.4 prior to administering treatment.**

Hypertension is an important AE associated with pazopanib. Frequent **blood pressure (BP) monitoring is important** in subjects receiving pazopanib versus placebo starting on day 8 and continuing until the subject is off study. Experience to date suggests that increases in BP may occur following dosing with pazopanib for a number of weeks and that these increases may occur relatively quickly. **Section 7.7** includes specific guidelines on the management of treatment-emergent hypertension. Recommendations for hypertension monitoring and management are presented in **Appendix F**.

QTc prolongation and Torsades de Pointes is a rare but serious adverse event associated with pazopanib. Therefore, the following is required:

- **Intensive QTc monitoring. A baseline ECG is required prior to study registration, and subjects with QTc \geq 480 msec are excluded.** Repeat ECG must be performed during the week 2. After surgery, for those subjects continuing on maintenance pazopanib, if the QTc interval at 4 weeks is \geq 500 msec, the ECG should be repeated within 7 days and, if the QTc interval remains \geq 500 msec, the subject should be removed from the study. Additionally, if the QTc interval is increased by 60 msec or more from baseline but the QTc interval remains at $<$ 500 msec, an ECG should be repeated within 7 days. If the repeat ECG again shows a \geq 60 msec increase in the QTc interval from baseline, consideration should be given to removing the subject from the study or increasing monitoring, after discussion with the Principal Investigator.
- **Subjects must be questioned about family history of prolonged QTc, personal history of prolonged QTc, relevant cardiac disease, and concomitant medications which are associated with a high risk of causing QTc prolongation prior to study registration.**
- **Concomitant treatment with drugs that are associated with a high risk of causing QTc prolongation should be changed to similar agents that do not pose such a risk, if possible, prior to a subject receiving the first dose of pazopanib.** A comprehensive list of agents that are associated with a risk of prolonging the QTc interval is provided in **Appendix E**.
- **Potassium, calcium, phosphate, and magnesium levels must be obtained before administration of the first dose of pazopanib and frequently thereafter (as described in the Study Calendar, Appendix A).**

- **Abnormalities that occur after enrollment in potassium, calcium, phosphate, and magnesium levels should be managed as follows:** Pazopanib should be held and an ECG must be performed for hypokalemia or hyperkalemia \geq grade 2; hypocalcemia or hypercalcemia \geq grade 3; hypophosphatemia \geq grade 3; hypomagnesemia or hypermagnesemia \geq grade 3. Grading is according to CTCAE v4. These laboratory values should be corrected as soon as possible in a manner consistent with good medical judgment. Pazopanib may be re-administered when hypokalemia or hyperkalemia is grade 1 or within institutional limits; hypocalcemia or hypercalcemia is \leq grade 2, hypophosphatemia is \leq grade 2; and hypomagnesemia or hypermagnesemia is \leq grade 2. Even though pazopanib administration is allowed at these lower grades, every effort should be made to correct the abnormal lab values to normal if possible.

If an ECG, obtained because of these lab values, reveals an increase in the QTc to >500 msec or an increase in the QTc by at least 60 msec from baseline, the ECG should be repeated before re-administration of pazopanib. If the QTc interval, on the repeat ECG, is still ≥ 500 msec, the subject should be removed from the study. If the QTc, on the repeat ECG, remains increased in the QTc by at least 60 msec from baseline but is less than 500 msec, consideration should be given to removing the subject from the study.

Renal function (creatinine and urinary protein) should be frequently monitored as suggested by the pathologic changes noted in animal studies and evidence from studies of other antiangiogenic agents. Specific guidelines for management of proteinuria and elevated creatinine are presented in **Section 7.7**.

Hepatic Function monitoring include ALT, AST, GGT, alkaline phosphatase and total bilirubin at the following visits:

- at screening;
- before initiation of pazopanib treatment;
- end of week 2;
- prior to Day 1 of each cycle;
- at post-treatment visit;
- final visit;
- 30-day follow-up

Periodic monitoring should continue monthly if pazopanib monotherapy is continued. Pazopanib is not recommended for subjects with severe hepatic impairment (defined as $>3 \times$ ULN, regardless of any level of ALT).

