7.6 Duration of Follow-Up

When a subject discontinues the study, a Final Visit will be conducted. All subjects will have one Follow-up Visit approximately 30 days after the Final Visit. This Follow-up Visit does not need to be performed for subjects who have had a Final Visit conducted \geq 30 days after discontinuation of maintenance pazopanib therapy.

Study visits and evaluations will be performed in clinic at Screening and within approximately 72 hours prior to hospital admission for each chemotherapy cycle (neoadjuvant as well as adjuvant). Assessments will include interval history, physical examination, blood counts and chemistries. Radiological assessments including FDG-PET CT, MRI of the primary tumor, and diagnostic CT chest will be performed prior to the 14 day Run-in period of pazopanib versus placebo. After the Run-in period, and prior to commencement of preoperative chemotherapy, subjects will undergo repeat FDG-PET CT and MRI of the primary tumor. After 2 cycles of chemotherapy, FDG-PET CT and MRI of the primary tumor will be repeated. (**Refer to Section 4.3 and Appendix A**). Study procedures may be performed up to approximately 72 hours before or after the scheduled visit date.

Subjects will be evaluated daily during radiation therapy. Following surgery, subjects who remain on pazopanib monotherapy will have study visits and evaluations monthly for the one year duration of therapy, and follow-up visits will be every 3 months for those not on pazopanib. CT of the chest without contrast will be performed every 3 months for the first

year following surgery and MRI (or CT) of the primary site of the tumor will be performed every 6 months.

Following the Final Visit and/or 30-day Follow-up Visit, follow-up will proceed as described in the study calendar (Appendix A) until recurrence or progression. Patients experiencing recurrence or progression will be contacted every 4 months for overall survival, unless the patient has withdrawn consent for the study has ended.

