7.7.1 Dose Interruptions/Modifications for Specific, Non-liver Related, Toxicities

Recommendations for pazopanib (investigational product, IP) dose interruptions/modifications in case of specific treatment-emergent AEs are provided in Table 1.

Table 1 Dose Modification Algorithms for Potential Treatment-Related Adverse Events

AE Terms & Descriptions	Dose Modification Algorithms
-------------------------	------------------------------

AE Terms & Descriptions	Dose Modification Algorithms
Hypertension	
(A). Asymptomatic and persistent SBP of ≥ 140 and < 170 mmHg, or DBP ≥ 90 and < 110 mmHg, or a clinically significant increase in DBP of 20 mmHg (but still below 110 mmHg).	
Step 1. Continue investigational product (IP) at the current dose.
 
Step 2. Adjust current or initiate new antihypertensive medication(s).
 
Step 3. Titrate antihypertensive medication(s) during next 2 weeks as indicated to achieve well-controlled^a blood pressure (BP). If BP is not well-controlled within 2 weeks, consider referral to a specialist and go to scenario (B).

(B). Asymptomatic SBP ≥ 170 mmHg, or DBP ≥ 110 mmHg, or failure to achieve well-controlled BP within 2 weeks in scenario (A).	
Step 1. Consider reducing or interrupting IP, as clinically indicated.
 
Step 2. Adjust current or initiate new antihypertensive medication(s).
 
Step 3. Titrate antihypertensive medication(s) during next 2 weeks as indicated to achieve well-controlled BP.
 
Step 4. Once BP is well-controlled, restart IP dose-reduced by 200 mg if IP was interrupted.

(C). Symptomatic hypertension or recurring SBP ≥ 170 mmHg, or DBP ≥ 110 mmHg, despite modification of antihypertensive medication(s)	
Step 1. Interrupt IP
 
Step 2. Adjust current or initiate new antihypertensive medication(s).
 
Step 3. Titrate antihypertensive medication(s) during next 2 weeks as indicated to achieve well-controlled BP. Referral to a specialist for further evaluation and follow-up is also recommended.
 
Step 4. Once BP is well-controlled, restart IP dose-reduced by 200 mg.

(D). Refractory hypertension unresponsive to above interventions.	Discontinue IP and continue follow-up per protocol.
Prolongation of QTc Interval: If the QTc is prolonged, the ECG should be manually read to ensure accuracy of the reading. The values below refer to manually-read ECGs. Refer to Section 7.1.1 for ECG monitoring	
QTc $\geq 480 < 500$ msec	Continue IP; monitor as clinically indicated.

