APPENDIX A: Study Activities and Treatment Calendar

	Screening	End of Week Two	Prior to Day 1 of each cycle	After 2 cycles of preop chemo	At time of surgery	Post-treatment follow-up every 4 weeks if receiving pazopanib, else every 3 months
Informed Consent	X					
History/Progress Notes	X	X	X			X
Physical Exam	X	X	X			X
Vitals signs	X	X	X			X
Performance Status	X	X	X			X
Treatment Toxicity		X	X			X
Pathology Review	X				X	
CBC, chemistries, Ca ⁺⁺ , phos, Mg ⁺ , hepatic panel	X	X	X			X
UA	X		X			X
Pregnancy test	X					
INR	X					
ECG	X	X				X (every 3 months)
ECHO	X					
Tissue/blood for correlative studies	X	X		X	X	X (every 3 months)
FDG-PET	X	X		X		
MRI	X	X		X		
Plasma pazopanib trough level		X (2 visits)				X (every 3 months)
Full plasma pazopanib PK (optional)						X (once during Weeks 2-4)
CT-chest	X					X (every 3 months)

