1.0 General Guidelines

1.1 Frequency of monitoring. Blood pressure (BP) should be monitored at least every 2 weeks for the duration of treatment. More frequent monitoring should be considered on a study by study basis, particularly during the first two cycles of pazopanib therapy.

1.2 Data recording. All required data should be recorded in the appropriate CRF or on the subject's blood pressure monitoring diary, as appropriate. **The following data are required at baseline and at each subsequent assessment:**

- Assessment date and time
- Pulse
- Systolic and diastolic BP (2 readings/assessment taken 5 minutes apart while subject sitting)

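### On maintenance pazopanib, the study calendar yields about half of the blood-pressure readings that Appendix F sets as a minimum, and it schedules none at Table 1's 2-week decision point

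*Combined protocol and SAP*

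**What the plan says.** Five places bear on how often blood pressure is taken.

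- **Section 7.1.1 (Precautions/Warnings)** singles out hypertension as an important adverse event and asks for frequent monitoring "in subjects receiving pazopanib versus placebo starting on day 8 and continuing until the subject is off study". It names no interval. In the same paragraph it sends the reader on: "Recommendations for hypertension monitoring and management are presented in" Appendix F.
- **Appendix F, 1.1** gives the only stated minimum: "Blood pressure (BP) should be monitored at least every 2 weeks for the duration of treatment". It adds: "More frequent monitoring should be considered on a study by study basis, particularly during the first two cycles of pazopanib therapy". No study-specific interval is then set. Item 1.2 lets data go in the CRF "or on the subject's blood pressure monitoring diary, as appropriate".
- **Appendix A** marks vital signs at screening, at the end of week two, before day 1 of each cycle, and in the column headed "Post-treatment follow-up every 4 weeks if receiving pazopanib, else every 3 months". It has no blood-pressure row of its own and no diary entry.
- **Section 7.6** says that "subjects who remain on pazopanib monotherapy will have study visits and evaluations monthly for the one year duration of therapy". Section 4.3 ties blood pressure to visits, so it adds nothing between them.
- **Section 7.7.1, Table 1 (hypertension, scenario A)** has antihypertensives adjusted and titrated, and then: "If BP is not well-controlled within 2 weeks, consider referral to a specialist and go to scenario (B". Scenario B is where reducing or interrupting pazopanib comes into consideration.

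**The concern.** Sites usually work from the calendar. One that does so during maintenance will take blood pressure less often than the protocol's own minimum, for an adverse event that drives pazopanib dose changes. A rise just after one 4-weekly visit could go unrecorded until the next. After a raised reading at a visit, the next scheduled one falls about 2 weeks after Table 1 needs an answer.

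Other safety tests in Section 7.1.1 do not have this gap: electrolytes are tied to the study calendar and hepatic tests have a list of visits. Blood pressure has neither.

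Safety profile is a secondary endpoint (Section 4.2.2). A site that follows Appendix F and one that follows Appendix A would detect hypertension with different completeness.

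**Working it through.** The documents state no number of blood-pressure readings, so there is no figure of theirs to reproduce. The check is a count. I use one reading to mean one monitoring occasion, since Appendix F 1.2 takes two measurements on each. I take the duration of treatment in Appendix F 1.1 to mean time on pazopanib.

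**Inputs**
- Maintenance length: 52 weeks (Section 7.0 treatment table).
- Minimum interval: 2 weeks (Appendix F 1.1).
- Scheduled interval: 4 weeks (Appendix A) or monthly, 12 in the year (Section 7.6).
- Early maintenance trough draws: one in Week 2 and one in Weeks 3-4 after restarting (Section 4.3). Blood pressure is taken at all visits unless otherwise indicated (Section 4.3).
- Run-in: 14 days, with two trough draws, one on any of Days 10-14 and one on the day of the repeat PET (Section 4.3; shown as 2 visits in Appendix A).

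**Maintenance**

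Minimum: 52 / 2 = 26.

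| Reading of the schedule | Scheduled | Short of 26 |
|---|---|---|
| Section 7.6, monthly | 12 | 14 / 26 = 54% |
| Appendix A, every 4 weeks | 52 / 4 = 13 | 13 / 26 = 50% |
| Appendix A plus Week 2 trough visit | 13 + 1 = 14 | 12 / 26 = 46% |
| Appendix A plus both early trough visits, if the second is separate from the Week 4 visit | 13 + 2 = 15 | 11 / 26 = 42% |

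The trough draws help only in the first month. From then on the scheduled gap is 4 weeks (or a month) against a minimum of 2.

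**Table 1, scenario A**

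Raised pressure found at a 4-weekly visit starts a 2-week titration window. The next scheduled visit is at 4 weeks, which is 4 - 2 = 2 weeks after the decision point. Appendix A places no assessment at that point.

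**Run-in**

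Minimum over 14 days: 14 / 14 = 1. The calendar gives at least 1 (end of week two) and can give more through the trough visits. The shortfall is 0. What does not match is the start: day 8 in Section 7.1.1 against a first on-treatment calendar reading on Days 10-14.

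**The case against.** The strongest reply is that the two appendices can both be followed. Appendix A lists clinic activities; Appendix F sets how often pressure is monitored and allows a diary. Four-weekly visits plus diary readings would meet the minimum. Appendix F is also phrased as a recommendation.

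This is right as far as it goes: the texts are compatible if home readings are taken. But no section requires them. The only diary Section 7.1.1 issues is for pazopanib dosing, the blood-pressure diary appears only in Appendix F with a discretionary qualifier, and the calendar omits it. A recommendation that is the only stated minimum still should not be undercut by the calendar.

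Four stronger inferences are tempting, and the documents do not support them.

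- **That three schedules conflict.** Section 7.1.1 gives a start and an end but no interval, and defers to Appendix F. Only two intervals disagree.
- **That half of all required readings are missed, including in the run-in.** The shortfall is confined to maintenance, which is optional and limited to pazopanib-arm patients with a partial response (Section 7.0, note G; Section 11.4). The run-in meets the minimum, and a reading as early as Day 10 is possible.
- **That Table 1's 2-week rule cannot be applied.** It is triggered by an event and itself calls for titration over the following 2 weeks, which implies follow-up readings. Nothing bars unscheduled checks. The accurate statement is that the calendar provides no visit for them.
- **That about 6 of 14 pazopanib patients are affected.** The arithmetic is 0.42 x 14 = 5.9, using the hypertension rate quoted in Section 2.4 from another trial. The 14 is the whole pazopanib arm, whereas the shortfall exists only among maintenance patients, whose number is not known in advance.

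**Conclusion.** The inconsistency is real and limited to maintenance. The calendar supplies 12 to 15 of the 26 readings that Appendix F's minimum implies, a shortfall of 42% to 54% depending on whether visits are monthly or 4-weekly and whether trough draws count. It also schedules no assessment at the point where Table 1 moves a patient from scenario A to B. In the run-in there is only the small mismatch between the day-8 start and the first calendar reading on Days 10-14.

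This rests on a full 52 weeks of maintenance and on counting only what the protocol schedules. Diary readings or unscheduled checks taken on a site's own initiative would narrow the gap, and sites may differ in that. The effect is on patient safety and on how completely hypertension is captured in the safety endpoint. The primary comparison, SUV change over the run-in, and its power are unaffected. The amendment is worth making but does not threaten the trial's main result.

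**What to change.** Reconcile Section 7.1.1, Section 7.6, Appendix A and Appendix F 1.1 to a single blood-pressure schedule and show it as its own row in Appendix A. State three things:

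1. the day monitoring starts in the run-in;
2. the interval in the run-in and in maintenance;
3. whether diary readings count toward the Appendix F minimum and toward Table 1 decisions and, if so, where they are recorded.

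Which schedule to adopt is a clinical choice for the investigators; the statistical request is only that all sites follow the same one. The cost is a wording and calendar amendment, and Appendix F already foresees the diary. The downside is possibly more readings for each maintenance patient.

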A complete physical examination will be performed at Screening, including height. A symptom-directed physical examination including weight will be performed at all other visits unless indicated otherwise. Clinically significant physical examination findings after the administration of the first day of dosing will be recorded as adverse events.

12-lead Electrocardiogram (ECG)

A resting 12-lead ECG will be performed at the Screening Visit, unless performed for standard of care within 14 days. The investigator or a designee will sign and date the ECGs, determine if any findings outside normal physiological variation are clinically significant (in consultation with a cardiologist if necessary), and document this on the ECG report. ECGs will also be performed at the initiation of pazopanib maintenance therapy, Cycle 1 Day 1 and Cycle 2 Day 2.

Vital Signs

Vital sign determinations of heart rate, blood pressure and body temperature will be measured at all visits unless indicated otherwise.

Pregnancy Test

For female subjects of childbearing potential, a serum pregnancy test will be performed at the Screening Visit and a urine pregnancy test will be done at the Run-in period Day 1 visit prior to the first dose of pazopanib versus placebo. Subjects considered not of childbearing potential must be documented as being surgically sterile or post-menopausal (for at least 1 year). The test results must be reviewed and determined to be negative prior to dosing. If the urine pregnancy test is positive at Cycle 1 Day 1, it should be confirmed by a serum pregnancy test. The test may be repeated at the discretion of the Investigator at any time during the study. Should the subject become pregnant or suspect she is pregnant while participating in this study, she should inform the Investigator immediately. The Principal Investigator should be notified and will be responsible for contacting the representative at Novartis.

Clinical Laboratory Tests

All subjects will undergo the laboratory assessments outlined in **Appendix A**. After Cycle 1 Day 1, clinical laboratory tests should be performed within 72 hours surrounding the scheduled study visit date. Any laboratory value outside the reference range that is considered clinically significant by the investigator will be followed as appropriate. Clinically significant laboratory values will be recorded as adverse events if they meet the criteria as specified in **Section 7.7**.

Tumor Assessments (Radiologic)

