QTc ≥ 500 msec	Discontinue IP and continue follow-up per protocol.
Proteinuria	
UPC <3	Continue pazopanib at the current dose; monitor as clinically indicated
UPC ≥ 3 or 24-h urine protein ≥ 3 g	
Step 1. Interrupt IP.
 
Step 2. Weekly UPC or 24-hr urine protein monitoring until UPC is <3 or 24-hr urine protein is <3 grams. Then restart pazopanib dose-reduced by 200 mg.
 
Step 3. If UPC ≥ 3 or 24-h urine protein ≥ 3g recurs, repeat steps 1 and 2.
 
Step 4. If UPC ≥ 3 or 24-hr urine protein ≥ 3g recurs and the pazopanib dose can no longer be reduced, discontinue pazopanib and continue follow-up per protocol.

Hemorrhage /Bleeding: Investigate and document underlying etiology of the bleeding	
Grade 1	For hemoptysis, interrupt pazopanib and contact the Novartis Study Physician to discuss whether further treatment with pazopanib is appropriate.

	For other Grade I hemorrhage/bleeding events, continue pazopanib at the current dose; monitor as clinically indicated.
Grade 2	Step 1. If pulmonary or GI bleed (other than hemorrhoidal bleeding), discontinue IP and continue follow-up per protocol. Otherwise, interrupt IP until the AE resolved to \leq Grade 1. Step 2. Restart IP; consider reducing dose and monitor as clinically indicated.
Grade 3 or 4, or Recurrent \geq Grade 2 event after dose interruption/reduction.	Discontinue IP and continue with follow-up per protocol.
Venous Thrombosis (DVT, PE)	
Grade 2	Continue IP at the current dose; monitor as clinically indicated
Grade 3	Step 1. Interrupt IP. Step 2. Initiate and monitor anticoagulation as clinically indicated. Step 3. Resume IP at same dose only if all of the following criteria are met: 
 • The subject must have been treated with anticoagulant at the desired level of anticoagulation for at least one week. • No Grade 3 or 4 or clinically significant Grade 2, hemorrhagic events have occurred while on anticoagulation treatment. Subject should be monitored as clinically indicated during anticoagulation treatment and after resuming study treatment. When treating with warfarin, international normalized ratio (INR) should be monitored within three to five days after any change in IP dosing (eg, re-initiating, escalating/de-escalating, or discontinuing IP), and then at least weekly until the INR is stable. The dose of warfarin (or its derivatives) may need to be adjusted to maintain the desired level of anticoagulation

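### For a maintenance QTc of 500 msec or more, Section 7.1.1 repeats the ECG with no hold while Table 1 stops pazopanib, neither says which governs dosing, and Appendix A omits the week-4 ECG that triggers the 7.1.1 rule

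*Combined protocol and SAP*

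**What the plan says.** Section 7.1.1 lists its QTc precautions as requirements. For the run-in it states "Repeat ECG must be performed during the week 2". For maintenance after surgery it sets a check at 4 weeks: if the QTc is 500 msec or more, "the ECG should be repeated within 7 days and, if the QTc interval remains" at or above that value, the subject is taken off the study.

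A separate item in 7.1.1 covers ECGs taken because of an electrolyte abnormality. Pazopanib is already held at that point. If the ECG shows a QTc above 500 msec, or a rise of at least 60 msec, "the ECG should be repeated before re-administration of pazopanib". Removal is required only if the repeat is still 500 msec or more.

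Section 7.7.1, Table 1, deals with the same event. Its QTc header asks for a manual reading and adds "The values below refer to manually-read ECGs" and "Refer to Section 7.1.1 for ECG monitoring". The action at 500 msec or more is "Discontinue IP and continue follow-up per protocol".

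On timing, Section 4.3 says "ECGs will also be performed at the initiation of pazopanib maintenance therapy, Cycle 1 Day 1 and Cycle 2 Day 2", in addition to screening. In Appendix A the relevant column is headed "Post-treatment follow-up every 4 weeks if receiving pazopanib, else every 3 months", but the ECG cell in that column limits ECGs to every 3 months.

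**The concern.** Two safety instructions apply to one drug at one threshold and ask for different actions. One acts on a single value, after the tracing has been read by hand. The other waits for a second ECG up to a week later and does not mention dosing in between. A site that works from 7.1.1 could keep giving pazopanib at a QTc of 500 msec or more until the repeat. A site that books ECGs from Appendix A could miss the ECG that starts the rule. The protocol itself describes QTc prolongation and Torsades de Pointes as rare but serious and asks for intensive monitoring.

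The two texts also differ on what happens to the patient. Section 7.1.1 ends study participation; Table 1 ends drug and keeps follow-up. Progression-free and overall survival are secondary endpoints (Section 4.2.2), so follow-up after drug is stopped has value.

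**Working it through.** The plan states no figure to reproduce. The check is a comparison of texts, with small arithmetic for size.

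**Action rules at a QTc of 500 msec**

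| | 7.1.1, maintenance week 4 | 7.1.1, electrolyte-triggered ECG | 7.7.1, Table 1 |
|---|---|---|---|
| Trigger | 500 msec or more | above 500 msec, or a rise of 60 msec or more | 500 msec or more, manually read |
| Drug meanwhile | not stated | already held | discontinued |
| Repeat ECG | within 7 days | before restarting | none |
| If the repeat is below 500 msec | no action stated at this threshold | restart implied | not applicable |
| If the repeat is 500 msec or more | off study | off study | not applicable |
| Follow-up | not stated | not stated | continues |

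Three things follow.

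1. The first and third columns differ on dosing. The manual reading in Table 1 re-examines the same tracing and is not a second ECG, so it does not turn Table 1 into the 7.1.1 rule.
2. The authors wrote an explicit hold in the electrolyte item and none in the week-4 item. The silence on dosing therefore cannot be assumed to mean a hold.
3. The electrolyte item implies that drug may resume after a first value above 500 msec. Table 1 has no restart and names no exception.

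**ECG schedule**

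| Source | ECGs listed |
|---|---|
| Section 4.3 | screening; maintenance start; Cycle 1 Day 1 and Cycle 2 Day 2 |
| Section 7.1.1 | baseline; run-in week 2; maintenance week 4 |
| Appendix A | screening; end of week two; every 3 months post-treatment |

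Appendix A carries neither the maintenance-start ECG nor the week-4 ECG. It gives no start point for its 3-monthly ECGs. If they are counted from maintenance start (an assumption), the first falls near week 13, and 13 − 4 = 9 weeks after the check in 7.1.1.

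Whether Section 4.3 supplies a week-4 ECG depends on what its cycles are. On a 28-day maintenance rhythm, Cycle 2 Day 2 is day 28 + 2 = 30. On the 21-day chemotherapy cycle, the only cycle length the protocol defines, it is day 21 + 2 = 23 of chemotherapy. Section 4.3 also uses Cycle 1 Day 1 for the pregnancy test done at run-in Day 1. The text does not settle the question.

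**Size**

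- Further doses if a site follows 7.1.1 alone: from 0 (repeat on the same day) to 7 (repeat on the last allowed day). At the full daily dose of 800 mg, the maximum is 7 × 800 = 5,600 mg.
- Patients: 21 planned, randomized 2:1, gives 21 × 2/3 = 14 on pazopanib. Under Section 11.4 only run-in responders who choose it continue, so 14 is an upper limit for maintenance.

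**The case against.** The strongest reply is that the two texts have separate jobs. Section 7.7 and Table 1 are the dosing rules, and the table sends the reader to 7.1.1 only for monitoring. On that reading Table 1 stops the drug, and 7.1.1 then decides on repeat ECGs and study removal. Section 7.1.1 never tells a site to continue dosing, and Section 7.8 lets the investigator stop drug for any adverse event. This reading is available, and continued dosing would require a site to overlook Table 1. But the protocol does not state it. Section 7.1.1 presents its QTc items as required, while 7.7 presents its modifications as recommendations, so a site could reasonably take 7.1.1 as the binding text.

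On study removal, Section 7.8 asks for end-of-treatment evaluations and for survival and recurrence follow-up of all patients, and it lists only study closure and patient decision as grounds for withdrawal. That reduces the practical harm, but the 7.1.1 wording still contradicts it.

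The electrolyte item can fairly be defended as a special case with a correctable cause and drug already held. It needs a label, not removal.

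A reader might also infer that Section 4.3 agrees with 7.1.1 and that Appendix A is the only outlier. The documents do not support this, because the Cycle 2 Day 2 visit may belong to the run-in, to chemotherapy or to maintenance. For the same reason it would be wrong to replace 4.3 with one merged schedule: if those are chemotherapy visits, ECGs during doxorubicin would be lost, and Section 10.3 describes early ECG and rhythm effects of that drug.

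**Conclusion.** The concern holds as a conflict between two safety instructions with no stated order of precedence, together with a calendar that leaves out an ECG on which one of them depends. It should be fixed. The possible excess is 0 to 7 daily doses, up to 5,600 mg, assuming full dose, no hold and a site that follows 7.1.1 alone. It concerns at most about 14 patients on maintenance. The documents give no rate of QTc at or above 500 msec, so the number actually affected is unknown.

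Two stronger readings should be resisted. A reader might infer that the protocol orders continued dosing at 500 msec; it is silent in 7.1.1 and says the opposite in Table 1. A reader might also infer that the trial's main result is at risk. The primary endpoint is the SUV change over the 14-day run-in (Section 14.1), measured before maintenance begins, so the maintenance conflict cannot affect it. The electrolyte item can apply during the run-in, but nothing in the documents shows an effect on the SUV comparison.

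**What to change.** - **Section 7.1.1, week-4 rule.** State that pazopanib stops on a manually read QTc of 500 msec or more, as in Table 1, and that any confirmatory ECG is taken off drug. At this threshold, replace removal from the study with Table 1's action, "Discontinue IP and continue follow-up per protocol".
- **Section 7.1.1, electrolyte rule.** Label it the exception for a corrected electrolyte abnormality, and name that exception in Table 1.
- **Appendix A.** Add ECGs at maintenance start and at maintenance week 4.
- **Section 4.3.** Keep the Cycle 1 Day 1 and Cycle 2 Day 2 ECGs, and say which cycles they belong to.

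The cost is wording in 4.3, 7.1.1, Table 1 and Appendix A. The two calendar entries are already called for elsewhere in the protocol, and the week-4 ECG fits the existing 4-weekly maintenance visit. The downside is that a patient with one transient reading loses maintenance drug, which Table 1 already provides.
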